## **V. Data Management and Statistical Analysis**

### Data Management

Data will be stored on servers that are protected by high-end firewall systems, data are encrypted so that information cannot be decoded, and IP addresses will not be collected (every computer that communicates over the Internet is assigned an IP address that uniquely identifies the device). Data files, once downloaded, will be stored on [name] password-protected computer located in her locked office.

### Statistical Analysis

The complex empirical methods described below will be conducted by [name], an experienced statistician and colleague of [name]. Data analysis will be performed using the SAS Software System. Descriptive statistics for all measurements will be estimated and reported. Frequency distributions will be created to screen for any errors and will be used to summarize categorical data; measures of central tendency and dispersion will be used to summarize continuous data. All data will be examined for bivariate relationships and results used to build a multivariate statistical model.

We will analyze our study data with an intent-to-treat and per protocol analyses. An intent-to-treat analysis includes all participants who were randomized, regardless of compliance, withdrawal, and anything that happens after randomization. An advantage is that it is an analysis based on original randomization; however, effect estimation may be conservative and misleading with increasing attrition. A per protocol analysis considers only participants who fully complied and completed the study. Per protocol is less conservative and may reflect true treatment differences for those with full compliance. Including an intent-to-treat and per protocol analysis will provide a more complete understanding of treatment effects. Because we will most likely encounter incomplete data due to dropouts and non-response, multiple imputation of missing data will be used to impute missing values based on other available covariates.

Outcomes, including victimization and frequency of risky dating behaviors and alcohol-protective behaviors will be modeled using a general linear mixed model. This is an appropriate statistical model to use with repeated measures data collected over time. A random effect for subject will be included to account for the multiple measurements taken at baseline and 6-month follow-up on each subject. Treatment group and demographics will be included as fixed effects in the model. Mediation models will be tested with a two-tiered approach for mediation testing, with bootstrapping to generate estimates of the indirect effect and 95% confidence intervals.

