## Baseline Assessment, Randomization, and Completion of RealConsent or Stress

### Management:

Once a participant is registered, she will get a confirmation email; her response will trigger another email that contains a link to the online baseline survey and a password for accessing. To enhance confidentiality of responses, we will encourage participants to choose a private location, use a secure, encrypted Internet connection, and close their web-browser after they have completed a survey. Once an individual completes the baseline survey, she will be randomized using an automated stratified block randomization program to either RealConsent-F or to Stress Management programs. Stratified block randomization will ensure equal numbers between conditions and that 125 participants from each university are assigned to each condition.

We will communicate to the research participants and encourage them to complete their assigned task (RealConsent-F or Stress Management) within two weeks. Participants can complete the modules at their own pace within the 2-week window and are able to leave a module and finish it later. Email prompts will be sent every 48 hours to remind participants to complete the modules. Participants will be contacted by email and/or text message prior to 6 months post-intervention (Spring 2019) to complete the posttest.

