### Sample Size

Primary outcome will be report of victimization; secondary outcomes are protective- and risk- related behaviors. Sample size is based on the number per group needed to detect clinically meaningful treatment effects on victimization. Calculations were based on 80% power, level of significance of .05, and two- tailed statistical tests. Clinically meaningful treatment efficacy was defined for our outcome variable as having between a small and moderate effect size (Cohen's  $h \geq .35$ ). This effect size was considered as a 9% point difference between groups, at a minimum, and could potentially translate to a clinically significant reduction in the number of victimizations on those college campuses that implement RealConsent. Based on previous research with female college students, assuming incidence of 0.22 without intervention and .13 with intervention, a total of 558 participants are needed (279 in each group). We expect 20% attrition based on previous work. To achieve adequate power, we estimate a needed sample size of at least 670; however, we are increasing sample size to 750 participants (375 in each group) to increase power.

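### The primary-outcome mixed model lists no time term, baseline adjustment or 6-month contrast; fitted as listed, it estimates half the effect the trial was sized on, with power below 80% under the planned attrition

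*Combined protocol and SAP*

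**What the plan says.** Section V, Statistical Analysis, is the only place where the model is specified. It assigns victimization and the behavioral outcomes to a general linear mixed model and gives two details. The first is the random part: "A random effect for subject will be included to account for the multiple measurements taken at baseline and 6-month follow-up on each subject". The second is the fixed part: "Treatment group and demographics will be included as fixed effects in the model". No time effect, treatment-by-time interaction, baseline covariate or 6-month contrast appears there or elsewhere, and no coefficient is named as the efficacy test. The section also says that bivariate results will feed into building a multivariable model. On missing data it says that "multiple imputation of missing data will be used to impute missing values based on other available covariates".

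Section III sets the order of events: "Once an individual completes the baseline survey, she will be randomized using an automated stratified block randomization program". The randomization is stratified so that each university contributes 125 women to each condition.

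Section V, Sample Size, rests on a two-group comparison of incidence: "assuming incidence of 0.22 without intervention and .13 with intervention, a total of 558 participants are needed". It uses 80% power and a two-sided 0.05 level, expects 20% attrition and enrols 375 per group.

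**The concern.** When the pre-randomization record is an outcome row in the same model, a treatment main effect is not the effect of treatment at follow-up. It is the arm difference averaged over both occasions, and at baseline the program cannot yet have acted. The sample size, by contrast, is for the whole difference at follow-up. A time main effect alone does not help, because the treatment coefficient is still the average over the two visits.

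Two things are at stake. If the listed terms are fitted, the primary estimate is about half the real 6-month effect, and a useful program could be declared ineffective. If the analyst adds terms later, the primary contrast is chosen after the fact, from candidates that differ widely in power. The same model sentence covers the secondary behavioral outcomes, so the dilution applies to them too.

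**Working it through.** **Inputs from the documents.** Rates 0.22 and 0.13; two-sided 0.05; 80% power; 375 randomized per arm; 20% loss, leaving 375 × 0.8 = 300 per arm with 6-month data; baseline survey before randomization; multiple imputation.

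**Inputs assumed, because the documents give neither.** Baseline rate p0 (0.10, 0.22 or 0.40) and correlation ρ between a woman's baseline and 6-month outcomes (0 to 0.5). At p0 = 0.40, ρ stops at 0.4, because binary outcomes with rates 0.40 and 0.13 cannot correlate above 0.47. Victimization is taken as yes/no, as the incidence figures imply.

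**1. The plan's own figure.** The two-proportion formula with pooled variance and no continuity correction gives 278.6, so 279 per group and 558 in total. This matches the plan. The power of that comparison is 80.05% at 279, 82.8% at 300 and 90.2% at 375 per group.

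**2. What the listed coefficient estimates.** (0 + 0.09)/2 = 0.045.

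**3. Power of the listed model.** Write v0 = p0(1 − p0) and v1 = p1(1 − p1). For n complete pairs per arm:

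variance = sum over arms of [v0 + v1 + 2ρ√(v0·v1)] / (4n), and power = Φ(0.045/SE − 1.96).

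With 375 baseline records, 300 follow-up records and imputation by arm and baseline outcome, the large-sample variance is the sum over arms of

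[v0/375 + v1(1 − ρ²)/300 + v1ρ²/375 + 2ρ√(v0·v1)/375] / 4.

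Example at p0 = 0.22, ρ = 0. Here v0 = 0.1716, and v1 = 0.1716 (control) and 0.1131 (intervention).
- Control: 0.1716/375 + 0.1716/300 = 0.0010296.
- Intervention: 0.1716/375 + 0.1131/300 = 0.0008346.
- Sum/4 = 0.000466, SE = 0.0216, and Φ(0.045/0.0216 − 1.96) = 55%.

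Simulation with 20 imputations and Rubin's rules (4,000 trials per setting) gave the figures in the first row below. Type I error from the same code, with 0.22 in both arms, was 4.8%.

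| Listed model, 375 randomized per arm | p0 = 0.10 | p0 = 0.22 | p0 = 0.40 |
|---|---|---|---|
| 20% loss, multiple imputation (the plan) | 65% to 53% | 55% to 42% | 48% to 38% |
| 20% loss, available records only | 59% to 42% | 45% to 31% | 38% to 28% |
| Full retention | 72% to 55% | 60% to 44% | 51% to 40% |

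Each range runs from ρ = 0 to ρ = 0.5 (0.4 at p0 = 0.40). Without imputation the coefficient shrinks further, because the extra 75 baseline-only records per arm carry no effect: 0.045 × 600/675 = 0.040 at ρ = 0, and 0.045 × 400/475 = 0.038 at ρ = 0.5. A random-intercept REML fit to simulated binary data agreed with the closed form to within about 3 percentage points.

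With complete pairs at p0 = 0.22, the listed coefficient would need 609 (ρ = 0) to 910 (ρ = 0.5) women per group for 80% power.

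**4. Alternatives, effect 0.09.**
- *6-month difference adjusted for baseline, 300 per arm.* Variance = sum of v1(1 − ρ²)/300. At ρ = 0, SE = 0.0308 and power is 83%. At ρ = 0.5, SE = 0.0267 and power is 92%.
- *Unconstrained treatment-by-time, 300 pairs per arm, p0 = 0.22.* Variance = sum of [v0 + v1 − 2ρ√(v0·v1)]/300. Power is 50% at ρ = 0 and 79% at ρ = 0.5. With the planned imputation it is about 55%, 69% and 82% at ρ = 0, 0.3 and 0.5; at p0 = 0.10 it is about 66%, 79% and 90%.

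**The case against.** The strongest reply is that nobody would fit the model this literally. The plan presents the mixed model as a method for repeated measures over time, gives the work to an experienced statistician and leaves room for model building, so the list of fixed effects may not be complete. It is true that the plan does not exclude the missing terms, and the halving is therefore conditional on fitting what is listed. But the plan does not supply those terms either, and model building from bivariate results leaves the choice to the data. The natural gap-filler, an unconstrained treatment-by-time test, is not safe: at low correlation it also misses 80%.

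A second reply is that the power figures depend on unstated inputs. They do. At full retention the listed model reaches 80.7% at a baseline rate of 0.05 (ρ = 0), and 80.0% to 86.5% at 0.02 (ρ up to about 0.3). Those settings contradict the plan's own 20% attrition. Under planned loss with imputation the best cases are about 79% (rate 0.02) and 74% (rate 0.05), so the shortfall can be small if baseline victimization is rare. The full-retention and available-records rows depart from the plan and serve only as bounds.

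Third, the arithmetic assumes a yes/no outcome on a linear scale. The 0.045 would not carry over unchanged to a logit model or a count score. Finally, constraining the baseline means is one valid repair among several; a baseline-adjusted 6-month contrast is enough.

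**Conclusion.** The concern holds. The primary efficacy contrast is not defined, and the terms that are listed test a quantity with half the effect the trial was sized on. The halving needs only the order of baseline and randomization, not the assumed inputs. The loss of power does depend on them: with the planned 20% loss (taken as random) and imputation, power is 38% to 65% for baseline rates of 0.10 to 0.40, and stays below 80% down to a baseline rate of 0.02. The risk is a missed or understated effect, or a primary contrast chosen after the data are seen. It is not a false-positive risk from the listed model. This should be settled before outcome data are analyzed.

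**What to change.** State the primary test, for example: *The primary analysis is the between-arm difference in victimization at 6 months, adjusted for baseline victimization and university (the randomization stratum).*

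If the mixed model is kept, add time and treatment-by-time, constrain the baseline means to be equal across arms, and name the 6-month treatment contrast as the primary test. Do not make an unconstrained treatment-by-time test primary. Use the same structure for the secondary outcomes, and state that the imputation model includes arm and baseline outcome.

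The cost is analysis-plan wording only: no new data and no new participants.

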### III. Methods

This study plans to conduct a randomized controlled trial with 750 female freshmen between 18-20 years of age from three universities in the state of Georgia (n=250 from each school) to test the efficacy of RealConsent-F compared to an attention-placebo comparison condition. Inclusion criteria for all proposed research activities are: female, aged 18-20 years, full time freshman, and single. Exclusion criteria are: other education levels, married, and/or graduate status. Participants will be randomized to either the intervention or attention-placebo study conditions. To control for Hawthorne effects, women in the RCT will be compared to women in an attention- placebo control condition—a general health promotion web-based program called “Stress Management.” Below are descriptions of the intervention, RealConsent and the attention-placebo program.

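### Randomization is balanced within university, but the efficacy model does not name university; if the universities differ in victimization, a group comparison is slightly conservative (minor)

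*Combined protocol and SAP*

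**What the plan says.** On allocation, the section on baseline assessment and randomization says: "Stratified block randomization will ensure equal numbers between conditions and that 125 participants from each university are assigned to each condition". Section III (Methods) gives the same layout, three universities with 250 participants each. The text does not state in so many words that university is the stratification factor, but the promised balance of 125 per condition within each university implies it.

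On analysis, the Statistical Analysis section uses a general linear mixed model for the outcomes, victimization included. The random part is for subject only: "A random effect for subject will be included to account for the multiple measurements taken at baseline and 6-month follow-up on each subject". The fixed part is given in one sentence: "Treatment group and demographics will be included as fixed effects in the model". The demographics are not listed, and neither this section nor Sample Size names university, site or stratum as a model term. The section also does not say whether the treatment effect is tested as a main effect, as a 6-month difference or as group by time.

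**The concern.** Stratified allocation keeps differences between universities out of the treatment comparison, because each university contributes equally to both arms. The analysis gets the benefit only if the model also takes those differences out of the error term. If university is left out, the residual variance still contains them. The reported standard error is then larger than the true sampling error, the test runs below its nominal 5%, and some power is lost. Sample Size raises enrolment to 750 expressly to gain power, so even a small avoidable loss is worth closing.

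**Working it through.** **Inputs from the documents.** Sample Size: "assuming incidence of 0.22 without intervention and .13 with intervention", 80% power, two-sided .05, 279 per group, 375 per group enrolled, and "We expect 20% attrition based on previous work". Randomization: three universities, equal arms within each.

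**Assumptions.** The documents give no university-specific rates. I take three sets of control rates averaging .22, a common risk ratio of .13/.22, and attrition that leaves the arms balanced within university.

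**Step 1: the plan's own figure.** With pooled variance, mean rate .175:

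n = [1.96 × √(2 × .175 × .825) + 0.8416 × √(.22 × .78 + .13 × .87)]² / .09² = 278.6, so 279 per group. The plan's figure reproduces.

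**Step 2: completers.** 375 × .80 = 300 per arm, and 300 / 3 = 100 per arm per university.

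**Step 3: type I error without university, 6-month outcome.** Total variance of a yes/no outcome at .22 is T = .22 × .78 = .1716. The between-university part B is the variance of the three rates, and the within part is W = T − B. The true sampling error reflects W but the model without university uses T, so the actual type I error is 2 × (1 − Φ(1.96 × √(T/W))).

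| Assumed control rates | B | W | √(T/W) | Type I, formula | Type I, simulated without / with university |
|---|---|---|---|---|---|
| .17/.22/.27 | .0017 | .1699 | 1.005 | 4.89% | 4.89% / 5.04% |
| .12/.22/.32 | .0067 | .1649 | 1.020 | 4.56% | 4.50% / 4.96% |
| .10/.20/.36 | .0115 | .1601 | 1.035 | 4.25% | 4.20% / 5.00% |

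The simulations are a linear model on the 6-month yes/no outcome, 200,000 trials per scenario. Independent repeats gave about 4.8%, 4.5% and 4.1% without university.

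**Step 4: power at .22 versus .13.** The standard error used without university is √((.22 × .78 + .13 × .87) / 300) = √(.2847 / 300) = .0308. The true one removes B from the control arm and B × (.13/.22)² from the intervention arm. For .12/.22/.32 that gives .2847 − .0067 − .0023 = .2757, and √(.2757 / 300) = .0303.

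- Without university: Φ((.09 − 1.96 × .0308) / .0303) = about 83.6%.
- With university: Φ(.09 / .0303 − 1.96) = about 84.3%.

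The simulations over all scenarios:

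| Assumed control rates | Mean SE without / with | SE overstated by | Power without / with | Loss (points) |
|---|---|---|---|---|
| .22/.22/.22 | – | – | 83.2% / 83.3% | 0.1 or less (simulation noise) |
| .17/.22/.27 | .03079 / .03067 | 0.4% | 83.02% / 83.25% | 0.2 |
| .12/.22/.32 | .03079 / .03033 | 1.5% | 83.34% / 84.14% | 0.8 |
| .10/.20/.36 | .03079 / .03000 | 2.6% | 83.67% / 85.00% | 1.3 |

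The equal-rates row comes from a separate run of the same design. By the formula in this step, power there is 83.2% with or without university.

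**Step 5: where the loss vanishes.** A group-by-time test compares within-subject changes. A university difference present at both waves cancels out of each change. In complete balanced data, a mixed-model fit gave the same group-by-time statistic with and without a university main effect.

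**The case against.** The strongest reply is that the loss depends on three conditions, none of which the documents settle: the universities must differ, university must not already be in the model, and the test must be a group comparison and not group by time. The larger losses also need wide gaps between three universities in one state: .32/.12 = 2.7-fold and .36/.10 = 3.6-fold. Power stays near 83% even without university. University might be intended as a demographic, or might enter through the model-building step: "All data will be examined for bivariate relationships and results used to build a multivariate statistical model". All of this stands as an argument about weight. It does not answer the point that the stratum is not prespecified. As written, whether it enters depends on how an undefined word is read or on what the data show.

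A reader might infer three stronger things, which the documents do not support.

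- **That the omission biases the result or invalidates the test.** Balance within university rules this out; the error is on the conservative side.
- **That the loss is larger in the two-wave model.** If that model is tested as a treatment main effect, with an assumed within-subject correlation of .2, the loss is 0.6 to 3.9 points. But the plan does not name that contrast. It averages in the pre-treatment wave, so its power is only about 42% to 46%, far from the 80% the trial is sized for. It is not a sound basis for judging weight.
- **That the model-building sentence brings follow-up mediators into the efficacy model.** Table 1 lists mediators apart from the outcomes, and they have their own analysis: "Mediation models will be tested with a two-tiered approach for mediation testing".

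**Conclusion.** The point holds as a minor one. University is the factor on which allocation is balanced, and it is not a prespecified term in the efficacy model. The consequence is conditional. If universities differ and the effect is tested as a group comparison, the standard error is overstated and the test is slightly conservative. On the 6-month outcome, type I error is about 4.9% to 4.1% and the power loss about 0.2 to 1.3 points over the range examined. Those sizes rest on assumed university rates, 300 completers per arm spread evenly over universities, and a linear model of the yes/no outcome. Any listed demographics that track university would shrink them. The sample size is unaffected.

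**What to change.** In Statistical Analysis, state that university (three levels) is a prespecified fixed effect in the primary and secondary efficacy models. If it was already meant as a demographic, naming it there is enough. The cost is two degrees of freedom out of about 600 completers and one sentence of text. No new data are needed, since university is known for every participant from randomization. If the universities turn out alike, or the effect is tested as group by time, including the term costs nothing measurable.

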### Sample Size

Primary outcome will be report of victimization; secondary outcomes are protective- and risk- related behaviors. Sample size is based on the number per group needed to detect clinically meaningful treatment effects on victimization. Calculations were based on 80% power, level of significance of .05, and two- tailed statistical tests. Clinically meaningful treatment efficacy was defined for our outcome variable as having between a small and moderate effect size (Cohen's  $h \geq .35$ ). This effect size was considered as a 9% point difference between groups, at a minimum, and could potentially translate to a clinically significant reduction in the number of victimizations on those college campuses that implement RealConsent. Based on previous research with female college students, assuming incidence of 0.22 without intervention and .13 with intervention, a total of 558 participants are needed (279 in each group). We expect 20% attrition based on previous work. To achieve adequate power, we estimate a needed sample size of at least 670; however, we are increasing sample size to 750 participants (375 in each group) to increase power.

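### Two figures in the sample-size paragraph contradict its own inputs: Cohen's h of .35 is not the 9-point effect (h = .24), and 670 does not cover 20% attrition (698 does)

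*Combined protocol and SAP*

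**What the plan says.** Everything at issue is in Section V, Sample Size, of the combined protocol and SAP.

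- **Design settings:** "Calculations were based on 80% power", "level of significance of .05, and two- tailed statistical tests".
- **Meaningful effect:** a Cohen's h of at least .35, described as lying between small and moderate. The next sentence adds: "This effect size was considered as a 9% point difference between groups, at a minimum".
- **Rates and evaluable number:** "assuming incidence of 0.22 without intervention and .13 with intervention", from which "a total of 558 participants are needed (279 in each group").
- **Attrition:** "We expect 20% attrition based on previous work".
- **Enrolment:** to keep adequate power, "we estimate a needed sample size of at least 670". The same sentence then raises the target to 750 (375 per group).

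Section III, Retention Activities, shows how to read the 20%. It reports response rates of 80% and 81% in a preliminary study and aims to retain at least 80%. The 20% is therefore a share of those enrolled.

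**The concern.** The paragraph gives one threshold in two forms, an h of .35 and a difference of 9 points, and treats them as the same. At the stated rates they differ. This is the plan's only definition of a clinically meaningful effect on victimization, the primary outcome. A result exactly at the design effect would meet the 9-point form and fail the h form. A reader who takes h at face value would also think the trial was sized for a larger effect than it was.

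The second problem is the allowance for attrition. The plan puts 670 forward as the smallest enrolment that keeps adequate power. If it is too low, a final enrolment between 670 and 697 could be accepted as sufficient when, at the plan's own attrition rate, it leaves fewer than the 558 completers the plan says it needs.

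**Working it through.** **Inputs, all from Section V, Sample Size:** p₁ = .22, p₂ = .13, two-sided α = .05 (z = 1.960), power 80% (z = 0.842), equal allocation, 20% attrition.

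**1. Reproduce the plan's 279.** Pooled two-proportion formula without continuity correction, with p̄ = (.22 + .13)/2 = .175:

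n per group = [1.960·√(2·.175·.825) + 0.842·√(.22·.78 + .13·.87)]² / .09² = 278.6, so 279, or 558 in total.

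This matches the plan exactly. The sample size therefore rests on .22 versus .13.

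**2. Cohen's h for those rates.**

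h = 2·asin(√.22) − 2·asin(√.13) = 0.239.

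The stated .35 is .35/0.2387 = 1.47 times this, an overstatement of 47%.

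**3. What h = .35 would mean.**

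- Down from .22: p₂ = sin²(asin(√.22) − .175) = .095, a difference of 12.5 points.
- Up to a control rate from .13: p₁ = sin²(asin(√.13) + .175) = .268, a difference of 13.8 points.
- Number needed: 2·[(1.960 + 0.842)/.35]² = 128.1, so 129 per group.
- At low incidence, a 9-point difference gives h = .35 only near .034 versus .124. Those are not the plan's rates.

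The 129 uses the arcsine formula and the 279 the pooled one. On a common basis the contrast is the same: arcsine, 276 versus 129; pooled, 279 versus about 132.

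**4. Attrition.**

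- The plan's figure: 558 × 1.20 = 669.6, so 670.
- Completers from 670: 670 × 0.80 = 536, or 268 per group.
- Attrition that 670 can absorb: 1 − 558/670 = 16.7%.
- Number needed for 20% loss: 558 / 0.80 = 697.5, so 698. The shortfall is 698 − 670 = 28.

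The choice of formula does not account for the gap. The smaller arcsine requirement of 276 per group gives 552 / 0.80 = 690, still above 670.

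**5. Power for .22 versus .13** (same pooled formula, two-sided .05, 20% loss):

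| Enrolled | Completers per group | Power |
|---|---|---|
| 670 | 268 | 78.4% |
| 698 | 279 | 80.1% |
| 750 | 300 | 82.8% |

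**The case against.** The strongest reply is that neither error changes the trial. The sentence that gives 670 goes on to set 750, and 750 is the target throughout: 250 per university in Section III, with further email batches if the first falls short, and 125 per university in each condition. No section makes 670 a point at which recruitment stops or is judged adequate. Even at exactly 670 enrolled, the loss is small, 78.4% against 80.1%. Likewise, the Statistical Analysis section has no success rule or test that uses h. The verbal label, between small and moderate, would suit an h of .24 as well. The h error also does not leave the trial too small, because the calculation used the smaller effect: if h = .35 were the true threshold, 300 completers per group would give about 99% power. Finally, the documents do not show whether the slip lies in h or in equating it with 9 points.

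Most of this stands as a limit on the consequences. The harm from a recruitment shortfall is possible but is not written into any rule. It does not remove either contradiction. The qualifier that 9 points is a minimum does not help, because the minimum itself has h = .24, below the stated floor of .35. The figure of 670 is offered as the floor for adequate power, and it does not provide the power stated. As to which form of the threshold to keep, the 9-point minimum is already the plan's own and is the one that produces its 279 per group, so keeping it imposes nothing new.

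**Conclusion.** The concern holds on both counts, as errors of statement and not of design. The design effect is h = 0.24, not .35. The enrolment needed for 558 completers at 20% attrition is 698, not 670. The 558 is correct, and the target of 750 is sufficient for .22 versus .13 with 20% loss.

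This rests on the plan's own rates, power, significance level and attrition, and on attrition being a fraction of those enrolled. The power figures are for the simple comparison of two proportions among completers that reproduces the plan's number. They do not address whether the assumed rates are realistic or how the planned mixed model would perform. The correction should be made because the figures concern the definition of a meaningful effect on the primary outcome and the stated floor for adequate power.

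**What to change.** In Section V, Sample Size:

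1. State that .22 versus .13 corresponds to a Cohen's h of about .24 and give that as the threshold, or keep the 9-point minimum difference and remove h. The second option is simpler, since the calculation was made from the rates.
2. Replace 670 with 698 and show the division: 558 / 0.80.
3. State that 750 enrolled with 20% attrition leaves 300 per group and about 83% power.

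The cost is a text correction. Enrolment and allocation do not change. The stated standardized effect becomes smaller, which describes correctly what the trial was sized to detect.
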